8.4.4 Baseline Descriptive Statistics

Baseline demographic characteristics will be reported overall and by arm.

8.4.5 Interim Analyses

Using the Haybittle-Peto approach, after 24 evaluable participants on each arm have undergone a total gastrectomy and found to have SRCCs, an interim evaluation will be performed. If at this interim point, the difference in the fractions of participants on the two arms with respect to the primary sensitivity endpoint is statistically different with $p < 0.001$, then the trial will stop accrual as soon as this can be determined, and the results will be reported based on these participants. As a result of selecting the very small 0.001 threshold, if the interim analysis does not find a difference at this level, the trial may continue to enroll participants until the intended 48 participants per arm, and the final evaluation will take place using the 0.05 significance level threshold (refer to Section **8.2**).

8.4.6 Analysis of the Exploratory Endpoints

- Determine if confocal endoscopic microscopy (CEM) will afford greater sensitivity for detection of SRC foci in *CDH1* germline mutation carriers compared to the Cambridge method
- To characterize gastric tract microbiota of *CDH1* germline mutation carriers.
- To access esophageal motility after total gastrectomy (in patients who pursue total gastrectomy)
- Apply machine learning for early gastric cancer detection via CEM and histopathology, and utilize image-to-image translation to enhance early cancer detection with CEM

The exploratory objectives are intended to collect data for use in planning future scientific investigations or clinical research. These analyses are expected to be performed primarily using descriptive techniques, reporting descriptive statistics including confidence intervals when appropriate. If any statistical tests are performed for evaluation of exploratory objectives, they will be done without formal adjustment for multiple comparisons, but in the context of the number of tests performed. We will tabulate separately by patient the crude cancer detection results for those

patients who undergo two procedures, and as an exploratory analysis, compare the results within patients and summarize results across patients using descriptive analyses.

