2.1.2 Re-Enrollment

2.1.2.1 Inclusion Criteria

- Subject must have previously been enrolled on the study and must have undergone endoscopy. Note: Subject may re-enroll only once after initial endoscopy performed
- Subject must have clinical need for a repeat endoscopy
- Prior on-protocol endoscopy must have occurred at least 6 months (+/- 2 weeks) and no greater than 18 months (+/- 4 weeks)

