2.3.2.3 Arm Assignment and Randomization

Subjects in Cohort 1 will be randomized by CRO to Arm 1 or Arm 2. No stratification is planned.

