3.3.1 Repeat Endoscopy

Endoscopy may be repeated once (per patient) for those with clinical need for repeat endoscopy at least 6 months (+/- 2 weeks) and no greater than 18 months (+/- 4 weeks) from the date of initial endoscopy on the current study. Patients who have been taken off study will be re-enrolled (refer to Section [2.1.2](#)).

Patient will be randomized for second endoscopy by CRO to Arm 1 or Arm 2.

Baseline assessment will be repeated as explained in Section [2.4](#).

Endoscopy will be performed as explained in Section [3.2](#)

Samples for correlative studies will be collected again as explained in Section [5](#).

Participants declining TG will be invited to Clinical Center to collect stool samples after second endoscopy (refer to Section [5](#)).

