Based on the prior experience with surveillance endoscopy, out of 110 patients, only 17+24=41 (37%) patients underwent a gastrectomy. To provide adequate patients to have a high probability of yielding 60 per arm who have a gastrectomy resulting in 48 with SRCCs, the study will randomize 175 patients to Bethesda protocol and 175 to Cambridge (350 total patients) in order to have 79% probability of obtaining 60 or more patients undergoing each procedure including gastrectomy, if the true probability of undergoing a gastrectomy is 37%. In practice, patients will continue to be randomized up to the limit of 350 total randomized patients, or until 48 patients on each arm have undergone a total gastrectomy and found to have SRCCs. Re-enrolled subjects will be counted separately at each enrollment/randomization.

All randomized patients who receive an endoscopy will have the crude cancer detection rates compared between the two methods. Data from a prior NIH trial indicated that the crude cancer detection rate was 15% using the Cambridge method and 36% using the Bethesda method, based on 26 and 109 evaluable patients respectively. In the present trial, if all 175 patients are required in each arm, then there would be 90.6% power to detect a difference with a two-sided 0.05 significance level between 15% and 30% crude cancer detection rates on the Cambridge method and the Bethesda protocol respectively. If only 135 evaluable patients undergo endoscopy using each method, there would be 81.0% power to detect a difference with a two-sided 0.05 significance level between 15% and 30% crude cancer detection rates.

Since January 2017 through September 2019, we have enrolled over 240 *CDH1* mutation patients on protocol 17-C-0043, performed over 145 surveillance endoscopies (12 performed in September 2019), over 61 risk-reducing gastrostomies (5 performed in September 2019). It is anticipated that more than 100 patients per year will be able to enroll onto this trial. Thus, accrual of up to 350 total subjects is expected to be completed in no more than 3.5 years.

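### The exploratory within-patient comparison in 8.4.6 is conditioned on who returns after a known first result, so a first-versus-second contrast is a biased estimate of the difference between methods

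*Combined protocol and SAP*

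**What the plan says.** Section 8.4.6 plans a per-patient table of crude detection for "patients who undergo two procedures, and as an exploratory analysis, compare the results within patients and summarize results across patients using descriptive analyses". It does not say whether pairs are split by sequence, whether pairs using one method twice are set apart, or how selective return is handled.

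Three other parts of the document determine what these pairs look like:

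- **Assignment.** Section 3.3.1: "Patient will be randomized for second endoscopy by CRO to Arm 1 or Arm 2". Section 2.3.2.3: "No stratification is planned". Writing B for Bethesda and C for Cambridge, four sequences arise: B-B, B-C, C-B and C-C.
- **Who returns.** Section 2.1.2.1: "Subject must have clinical need for a repeat endoscopy". The prior endoscopy must lie 6 to 18 months back, with small windows. Section 3.3 has pathology results discussed about two weeks after the endoscopy, so they are known before any return.
- **Counting.** Section 8.2: "Re-enrolled subjects will be counted separately at each enrollment/randomization".

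**The concern.** In a within-patient table each patient seems to serve as their own control. That holds only if being in the table does not depend on one of the two results. Here it does. The first result is known when gastrectomy is chosen and when the need for a repeat is judged, and a patient without a stomach cannot return for gastric biopsy. If patients with a positive first biopsy return less often than those with a negative one, the first method's detection rate among returners is too low. The B-minus-C difference then shrinks in B-C pairs and grows in C-B pairs. Same-method pairs would also appear to change although the method did not.

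What is at stake is limited. Section 8.4.6 says that the exploratory data are meant for planning later research, so a distorted difference could be carried into that planning.

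**Working it through.** **The plan's own figures.** Section 8.4.6 gives none. Section 8.2 does for the related secondary comparison: "then there would be 90.6% power to detect a difference with a two-sided 0.05 significance level between 15% and 30% crude cancer detection rates" at 175 per arm, and "If only 135 evaluable patients undergo endoscopy using each method, there would be 81.0% power to detect a difference". Exact enumeration of the two-sided Fisher test gives 90.65% and 80.99%, so both reproduce. They are not in question.

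**Inputs** (background series, sections 1.2.2 and 8.2)

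- First-examination positives: B 29/81 = 35.8%, C 4/29 = 13.8%. Difference 22.0 points.
- Gastrectomy after B: 24, of whom 13 were biopsy-positive. So 13/29 positives and 11/52 negatives, leaving 16 positives and 41 negatives.
- Gastrectomy after C: 17, of whom 2 were biopsy-positive. So 2/4 positives and 15/25 negatives, leaving 2 positives and 10 negatives.

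**Assumptions** (not in the documents). Everyone without gastrectomy returns. The two examinations are independent given SRCC status. There is no true order effect. SRCC prevalence π is between 80% (section 8.2) and 100%; section 1.2.1 gives 86%.

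**Formulas.** Let p1 and p2 be the detection rates of the first and second method, and rP and rN the return probabilities after a positive and a negative first result.

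- First-examination positivity among returners: F = p1·rP / [p1·rP + (1 − p1)·rN]
- Second-examination positivity among returners: S = (p2/π) · [p1·rP + (π − p1)·rN] / [p1·rP + (1 − p1)·rN]. At π = 100%, S = p2.

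**Results under the gastrectomy counts** (π = 100%; π = 80% in brackets)

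- F after B = 16/57 = 28.1%, not 35.8%. F after C = 2/12 = 16.7%, not 13.8%.
- B-C: 28.1 − 13.8 = 14.3 points (28.1 − 13.4 = 14.7).
- C-B: 35.8 − 16.7 = 19.1 points (36.1 − 16.7 = 19.4).
- Return is 57/81 = 70.4% after B and 12/29 = 41.4% after C, so B-C makes up 70.4/(70.4 + 41.4) = 63% of mixed pairs. Weighted mean: 0.63 × 14.3 + 0.37 × 19.1 = 16.1 points (16.4), against 22.0.
- B-B: 35.8 − 28.1 = +7.7 points (+6.7). C-C: 13.8 − 16.7 = −2.9 points (−2.8).
- Second endoscopies compared by their own randomized arm: 22.0 points (21.3 among those first assigned B, 22.2 among those first assigned C).

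With the planning rates of 30% and 15% and π = 86%, the same return pattern gives +8.3 (B-C), +12.1 (C-B) and a weighted mean of 9.7 points, against 15.

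**Range.** Let k = rP/rN, the same after both methods, with background rates and π = 100% (80% in brackets):

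| k | B-C | C-B | Equal-weight mean |
|---|---|---|---|
| 0 | −13.8 (−11.9) | +35.8 (+34.4) | 11.0 (11.3) |
| 0.25 | −1.6 (−0.3) | +32.0 (+30.9) | 15.2 (15.3) |
| 0.5 | +8.0 (+8.8) | +28.4 (+27.7) | 18.2 (18.2) |
| 1 | +22.0 | +22.0 | 22.0 |
| 1.5 | +31.8 (+31.2) | +16.4 (+17.0) | 24.1 (24.1) |

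For k from 0 to 1, the second-endoscopy contrast by its own arm stays between 19 and 22 points.

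**When B-C reverses.** At π = 100%, reversal needs k below (4/25)/(29/52) = 0.29. For 36% against 15% the limit is (0.15/0.85)/(0.36/0.64) = 0.31. The counts imply k = (16/29)/(41/52) = 0.70 after B and (2/4)/(10/25) = 1.25 after C, the latter on four positives.

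**The case against.** The strongest reply is that section 8.4.6 names no Bethesda-minus-Cambridge contrast, test, model or decision. A descriptive table of two results per patient is a legitimate repeatability summary. This stands, and it is why the point is minor. It does not remove the selection, and the wording leaves it open to summarize first-versus-second differences across all pairs.

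A reader might also infer four stronger things that the documents do not support:

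- **That the comparison reverses the difference between methods.** This needs first-positives to return at less than about 0.3 times the rate of first-negatives. The gastrectomy counts do not suggest it. It is an extreme bound.
- **That method is confounded with order.** This is true inside one sequence. Because the second endoscopy is randomized again, an additive order effect cancels when B-C and C-B are equally common. At the 63:37 split above, an assumed 10-point order effect leaves 10 × (0.37 − 0.63) = −2.6 points.
- **That the randomized second endoscopies go unused.** Sections 8.2, 8.3 and 8.4.3, read together, already bring them into the secondary crude-detection comparison under their own arm. Only a separate display among re-enrolled patients is missing.
- **That same-method pairs must improve.** The Cambridge counts point to a fall, though on four positives.

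**Conclusion.** The point holds as a minor one. A first-versus-second contrast among returners is a biased estimate of the difference between methods, because return follows a known first result. Under return implied by the gastrectomy counts it is about 16 points instead of 22, roughly a quarter too small, with spurious changes in same-method pairs. The size rests on everyone without gastrectomy returning and on examinations being independent given SRCC status. The direction is not fixed: if first-positives return more often than first-negatives, the average contrast is inflated (about 24 points at k = 1.5). The requirement of clinical need adds selection whose direction is unknown. With equal allocation at the second randomization, about half of the pairs carry no contrast between methods. The primary and secondary conclusions are not affected.

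**What to change.** In section 8.4.6:

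1. Tabulate pairs by randomized sequence (B-B, B-C, C-B, C-C), with the numbers returning by first arm and first biopsy result.
2. For any comparison of methods among re-enrolled patients, compare detection at the second endoscopy by the second randomized arm, within first arm and, where numbers allow, within first result.
3. Report same-arm pairs as repeatability only.
4. State that first-versus-second differences are not evidence about method, because returners are a selected group.

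This changes SAP wording only and needs no new data or patients. The cost is small strata (up to eight cells if first arm, first result and second arm are all crossed), so the results stay descriptive. They also apply to patients who return, not to everyone randomized.

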9 HUMAN SUBJECTS PROTECTIONS

9.1 RATIONALE FOR SUBJECT SELECTION

Subjects from all racial/ethnic groups are eligible for this study if they meet the eligibility criteria. Efforts will be made to extend accrual to a representative population.

9.2 PARTICIPATION OF CHILDREN

Children are excluded from this study because endoscopic screening for *CDH1* mutation carriers is not recommended in children.

9.3 PARTICIPATION OF SUBJECTS UNABLE TO GIVE CONSENT

Adults unable to give consent are excluded from enrolling in the protocol.

9.4 RISK/BENEFIT ASSESSMENT FOR ALL PARTICIPANTS

9.4.1 Known Potential Risks

9.4.1.1 Risks of Upper Endoscopy

The risks of upper endoscopy include, but are not limited to, temporary throat soreness, gastrointestinal bleeding, and rarely gastrointestinal perforation.

9.4.1.2 Risks of Fluorescein Intravenous Administration

The risks of intravenous administration of the contrast agent fluorescein are: nausea, vomiting, dizziness, headache, and low blood pressure.

9.4.1.3 Risks of General Anesthesia

The risks of general anesthesia include, but are not limited to, temporary confusion and memory loss, dizziness, difficulty passing urine, bruising or soreness from the IV drip, nausea and vomiting, shivering and feeling cold, sore throat, heart attack, pneumonia and stroke.

9.4.1.4 Risk of Biopsies

All care will be taken to minimize risks that may be incurred by tumor sampling. Biopsies will be taken during endoscopy. All procedure-related risks (such as bleeding, infection and visceral injury) will be explained fully during informed consent.

9.4.1.5 Risks of Esophageal Manometry

The risks of esophageal manometry include discomfort from passing a plastic tube through the nostril and possible bleeding.

9.4.1.6 Risks of Oropharyngeal Swabs and Salvia Collection

There are no risks or complications associated with an oropharyngeal swab (cheek cells) or saliva collection. The oropharyngeal swab test may cause momentary gagging because the back of the throat is a sensitive area, but it shouldn't be painful.

9.4.1.7 Risk of Losing Data

This includes the risk that data obtained during this study that can be released to members of the public, insurers, employers, or law enforcement agencies. Although there are no plans to release

results to the patients, family members or health care providers, this risk will be included in the informed consent document

9.4.1.8 Risks from Questionnaires

Questionnaires may contain questions that are sensitive in nature. The patients are asked to only answer questions they are comfortable with.

9.4.2 Known Potential Benefits

The benefit is detection of gastric cancer at its earliest stage so that it is potentially curable.

9.4.3 Assessment of Potential Risks and Benefits

A number of clinically appropriate strategies to minimize risks to patients have been built into the protocol through the means of inclusion/exclusion criteria, monitoring strategies, and management guidelines. Overall, the potential benefit of the study interventions in subjects with *CDH1* germline mutations outweigh the risks associated with study interventions.

The potential benefit to a patient that participates in this study is detection of gastric cancer at its earliest stage so that it is potentially curable.

Potential adverse reactions attributable to the study interventions are discussed in Section [9.4.1](#). All care will be taken to minimize side effects, but they can be unpredictable in nature and severity.

9.5 CONSENT PROCESS AND DOCUMENTATION

The informed consent document will be provided as a physical or electronic document to the participant or consent designee(s) as applicable for review prior to consenting. A designated study investigator will carefully explain the procedures and tests involved in this study, and the associated risks, discomforts and benefits. In order to minimize potential coercion, as much time as is needed to review the document will be given, including an opportunity to discuss it with friends, family members and/or other advisors, and to ask questions of any designated study investigator. A signed informed consent document will be obtained prior to entry onto the study.

The initial consent process as well as re-consent, when required, may take place in person or remotely (e.g., via telephone or other NIH approved remote platforms used in compliance with policy, including HRPP Policy 303) per discretion of the designated study investigator and with the agreement of the participant/consent designee(s). Whether in person or remote, the privacy of the subject will be maintained. Consenting investigators (and participant/consent designee, when in person) will be located in a private area (e.g., clinic consult room). When consent is conducted remotely, the participant/consent designee will be informed of the private nature of the discussion and will be encouraged to relocate to a more private setting if needed.

Consent will be documented with required signatures on the physical document (which includes the printout of an electronic document sent to participant) or as described below, with a manual (non-electronic) signature on the electronic document. When required, witness signature will be obtained similarly as described for the investigator and participant.

Manual (Non-Electronic) Signature on Electronic Document:

When a manual signature on an electronic document is used for the documentation of consent at the NIH Clinical Center, this study will use the following to obtain the required signatures:

- Adobe platform (which is not 21 CFR Part 11 compliant); or,

- iMedConsent platform (which is 21 CFR Part 11 compliant)

During the consent process, participants and investigators will view individual copies of the approved consent document on screens at their respective locations (if remote consent); the same screen may be used when in the same location, but is not required.

Both the investigator and the participant will sign the document using a finger, stylus or mouse.

Note: Refer to the CCR SOP PM-2, Obtaining and Documenting the Informed Consent Process for additional information (e.g., verification of participant identity when obtaining consent remotely) found at:

<https://ccrod.cancer.gov/confluence/pages/viewpage.action?pageId=73203825>.

10 REGULATORY AND OPERATIONAL CONSIDERATIONS

10.1 STUDY DISCONTINUATION AND CLOSURE

This study may be temporarily suspended or prematurely terminated if there is sufficient reasonable cause. Written notification, documenting the reason for study suspension or termination, will be provided by the suspending or terminating party to study participants. If the study is prematurely terminated or suspended, the Principal Investigator (PI) will promptly inform study participants, the Institutional Review Board (IRB) and will provide the reason(s) for the termination or suspension. Study participants will be contacted, as applicable, and be informed of changes to study visit schedule.

Circumstances that may warrant termination or suspension include, but are not limited to:

- Determination of unexpected, significant, or unacceptable risk to participants
- Insufficient compliance to protocol requirements
- Data that are not sufficiently complete and/or evaluable
- Determination that the primary endpoint has been met
- Determination of futility

Study may resume once concerns about protocol compliance, and data quality are addressed, and satisfy the IRB.

10.2 QUALITY ASSURANCE AND QUALITY CONTROL

The clinical site will perform internal quality management of study conduct, data and biological specimen collection, documentation and completion. An individualized quality management plan will be developed to describe the site's quality management.

Quality control (QC) procedures will be implemented beginning with the data entry system and data QC checks that will be run on the database will be generated. Any missing data or data anomalies will be communicated to the site(s) for clarification/resolution.

Following written Standard Operating Procedures (SOPs), the monitors will verify that the clinical trial is conducted and data are generated and biological specimens are collected, documented (recorded), and reported in compliance with the protocol, International Council on Harmonisation Good Clinical Practice (ICH GCP), and applicable regulatory requirements (e.g., Good Laboratory Practices (GLP), Good Manufacturing Practices (GMP)).

The investigational site will provide direct access to source data/documents, and reports for the purpose of monitoring and inspection by local and regulatory authorities.

10.3 CONFLICT OF INTEREST POLICY

The independence of this study from any actual or perceived influence is critical. Therefore, any actual conflict of interest of persons who have a role in the design, conduct, analysis, publication, or any aspect of this trial will be disclosed and managed. Furthermore, persons who have a perceived conflict of interest will be required to have such conflicts managed in a way that is appropriate to their participation in the design and conduct of this trial. The study leadership in conjunction with the National Cancer Institute (NCI) has established policies and procedures for all study group members to disclose all conflicts of interest and will establish a mechanism for the management of all reported dualities of interest.

10.4 CONFIDENTIALITY AND PRIVACY

Participant confidentiality and privacy is strictly held in trust by the participating investigators, and their staff. This confidentiality is extended to cover testing of biological samples and genetic tests in addition to the clinical information relating to participants. Therefore, the study protocol, documentation, data, and all other information generated will be held in strict confidence. No information concerning the study or the data will be released to any unauthorized third party without prior written approval.

All research activities will be conducted in as private a setting as possible.

The study monitor, representatives of the Institutional Review Board (IRB), and/or regulatory agencies may inspect all documents and records required to be maintained by the investigator, including but not limited to, medical records (office, clinic, or hospital) and pharmacy records for the participants in this study. The clinical study site will permit access to such records.

The study participant's contact information will be securely stored at the clinical site for internal use during the study. At the end of the study, all records will continue to be kept in a secure location for as long a period as dictated by the reviewing IRB or Institutional policies.

Study participant research data, which is for purposes of statistical analysis and scientific reporting, will be stored at the NCI CCR. This will not include the participant's contact or identifying information. Rather, individual participants and their research data will be identified by a unique study identification number. The study data entry and study management systems used by the clinical site and by NCI CCR research staff will be secured and password protected. At the end of the study, all study databases will be archived at the NIH.

To further protect the privacy of study participants, a Certificate of Confidentiality has been issued by the National Institutes of Health (NIH). This certificate protects identifiable research information from forced disclosure. It allows the investigator and others who have access to research records to refuse to disclose identifying information on research participation in any civil, criminal, administrative, legislative, or other proceeding, whether at the federal, state, or local level. By protecting researchers and institutions from being compelled to disclose information that would identify research participants, Certificates of Confidentiality help achieve the research objectives and promote participation in studies by helping assure confidentiality and privacy to participants.

